### **5.3 Definitions of Events**

- Airway maneuver: consists of either airway maneuvers such as chin lift, jaw thrust, submental pressure, mask ventilation, pushing downward on the mask, tightening of the strap, flexing the head forward or the insertion of a nasal or oral airway, supraglottic device, or ETT
- Oxygen desaturation:  $SpO_2 \le 90\%$  for  $\ge 15$  seconds
- Cardiac complications is defined by a change in either SBP or DBP > 25% from baseline, a change in heart rate > 25% from baseline, arrhythmias, and ST-changes on EKG (ST depression or elevation).
- Full recovery is defined as the time from endoscope withdrawal until a MOAA/S score of 5 was achieved and the patient could drink liquids and ambulate independently.
- Full recovery until actual discharge is defined as the interval from full recovery until the patient exited the recovery room.
- Induction to full sedation is the time from initial administration of intravenous sedative or analgesic to the insertion of the endoscope
- Intraprocedural period was defined as the time of first scope insertion until the last scope removal.
- Procedural interruption is defined as the removal of the endoscope due to a respiratory complication
- Modified Observer's Assessment of Alertness/Sedation Scale (MOAAS) from 1 5

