# **Endpoints of Interest**

- 1. Compare the amount of propofol administered during induction and total dose administered for procedure
- 2. Compare Modified Observer's Assessment of Alertness/Sedation Scale (MOAAS) scores immediately prior to endoscopic intubation and during the procedure

Protocol #: IU IRB# 1810997768 Date: 31AUG21 Page 5 of 17

- 3. Compare the length of time from induction to endoscopic insertion
- 4. Compare the incidence and duration of procedural interruptions (ie: number of times and length of time the endoscope is removed from the patient)
- 5. Compare the incidence, duration, and reason for airway maneuvers
- 6. Compare the length of time for the procedure (ie: length of time from procedure start to procedure end)
- 7. Compare recovery times
- 8. Compare patient satisfaction scores (visual analog scale (VAS)) immediately after procedure
- 9. Compare patient satisfaction scores 48 hours later
- 10. Compare patient tolerance to SuperNO2VA EtCO2 compared to control (ie: nasal cannula at 10LPM)
- 11. Compare endoscopist satisfaction scores for
- 12. Compare anesthesiologists satisfaction scores
- 13. Compare the incidence of cardiac complications

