Continuous positive airway pressure (CPAP), applied nasally or via facemask, has been shown to be more effective at minimizing hypoxia than other devices under sedation or general anesthesia. However, it requires a special mask and CPAP machine with high-fresh gas flows which may not be routinely equipped in GI endoscopy suites due to space and cost constraints. Therefore, a simplified CPAP system could be a surrogate for a conventional CPAP machine for procedures requiring sedation or general anesthesia with spontaneous breathing via a natural airway. Recently, a simple, novel CPAP device was developed, which includes a sealed nasal mask and disposable, flow-inflating hyperinflation bag (SuperNO2VA Et™ Satellite Set, Revolutionary Medical Devices, USA). A small pilot study by Ghebremichael, et al. demonstrated safety and efficacy with the use of the SuperNO2VA Et™ device for nasal mask ventilation (NMV) in anesthetized and paralyzed patients. The objective of our study is to compare oxygenation in spontaneously ventilating obese patients or those with diagnosed or undiagnosed OSA undergoing endoscopic ultrasound under propofol based sedation in an ambulatory surgical center between the SuperNO2VA Et™ nasal positive airway pressure (PAP) device and routine care with nasal cannula for O2 supply. In a simulated patient setup, the SuperNO2VA ET CO2Nasal mask are accurate for measurements of end tidal carbon dioxide (etCO2).

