### 5.2 Methods:

This study involves the oxygenation, continuous positive airway pressure, and ventilation of a subject via nasal mask and oxygenation via a closed facemask. The interventions directly related to this study are that of supplement oxygen, bag-mask ventilation, and continuous nasal CPAP intra-operatively and in the Post Anesthesia Care Unit.

Patients will be randomized in groups of ten to one of two groups using a random number table. Group A: Standard care with a nasal cannula. Group B: SuperNO2VA™EtCO2.

For each anesthetic case, a preoperative history and physical and intraoperative record will be documented (table 1).

Table 1: General Patient characteristics	
Age (years)	
Gender (M/F)	
Height (cm)	
Weight (kg)	
BMI (kg/m  )	
ASA classification (I-III)	
Diagnosed OSA on home CPAP	
Diagnosed OSA not on home CPAP	
STOP-BANG Score	
Patient Co-morbidities*	

\*Co-morbidities include any history of: hypertension, diabetes, coronary disease, valvular disease, arrhythmia, cerebrovascular disease, active cancer, tobacco use, pulmonary disease, renal disease, liver disease.

Once in the endoscopy suite, the patients will have continuous monitoring of heart rate, end tidal CO2 (EtCO2), O2 saturation, and every 2-minute BP monitoring. Patients randomized to group A, the anesthesia provider will supply oxygen via nasal cannula at 10LPM. Patients randomized to group B, the anesthesia provider will attach the SuperNO2VAM EtCO2's circuit port to the hyperinflation bag with the oxygen flow rate to 10 L/min, and the APL valve completely closed. Initial dosing bolus 0.5-1.0 mg/kg actual body weight of Propofol will be administered for sedation and MOAA/S scores will be assessed. Nursing or the research assistant will then record the patient's MOAA/S score. If the patient's MOAA/S score of <4 reached. Once a MOAA/S score of <4 is reached the endoscopist will perform endoscopic intubation and the goal will be to maintain a MOAA/S score of <4 until the procedure is over. If the patient's MOAA/S score  $\geq 4$ , additional 10 – 40mg bolus of propofol will be administered every 30–90 seconds until the

Protocol #: IU IRB# 1810997768 Date: 31AUG21 Page 9 of 17

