MOAA/S is <4. The measurements that will be made are the following: the incidence, severity, and time of oxygen desaturation, number of airway maneuvers performed, duration of airway maneuvers, reason for performing the airway maneuver, the onset time of administration of sedation, the duration of the procedure, the total dosage of the medication, vital signs - blood pressure, heart rate, and oxygen saturation, the time to full recovery, and patient cooperation. Nursing or the research assistant will document their patient's depth of sedation, cooperation with procedure, and safety. Patients will recover in the endoscopy suite. The patients will have continuous monitoring of heart rate, end tidal CO2 (EtCO2), O2 saturation, and every 5-minute BP monitoring and MOAAS Score. The time to discharge will be obtained for each patient. Patients will also complete a satisfaction and pain questionnaire before they are discharged. Patients will also be asked to complete another questionnaire within 48 hours concerning their satisfaction and their subjective degree of impairment due to the sedation either with a paper form and self-addressed envelope or electronically sent via e mail. If the patients do not complete their questionnaire, someone will contact them by telephone to collect the data. A statistician using student T-test, Fishers exact test, and other statistical methods they deem appropriate will analyze the collected data.

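### The airway-maneuver definition counts mask and strap adjustments, which gives the device arm extra ways to score on a secondary endpoint

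*Protocol*

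**What the plan says.** Airway maneuvers are item 5 of the 13 secondary endpoints, both in the Protocol's Summary Table and under Endpoints of Interest in Section 1: "Compare the incidence, duration, and reason for airway maneuvers".

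Section 5.3 gives a single definition for both arms. It is an open list of examples. Beside jaw, chin and head positioning and the insertion of airway devices, it contains mask ventilation and also "pushing downward on the mask, tightening of the strap".

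The interfaces differ by arm. For Group A, Section 5.2 says "the anesthesia provider will supply oxygen via nasal cannula at 10LPM". Group B receives the study device, described in Section 2 as one "which includes a sealed nasal mask and disposable, flow-inflating hyperinflation bag".

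Section 5.2 lists what is measured: "number of airway maneuvers performed, duration of airway maneuvers, reason for performing the airway maneuver". The type of maneuver is not on that list. Neither Protocol 10.3 nor SAP 1.3 mentions airway maneuvers, and neither separates device handling from airway opening.

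Section 5.4 lets patients cross over in either direction. Protocol 10.3 and SAP 1.3 call for both per-protocol and intention-to-treat analyses.

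**The concern.** Pressing on the mask and tightening its strap are adjustments of the interface that Group B wears from the start. A Group A patient on a cannula has no strapped mask to adjust, and the definition names no counterpart such as repositioning the cannula. One count therefore mixes two things: how often the airway had to be opened or supported, and how often the mask had to be re-seated.

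If the two arms need airway opening equally often, the device arm can still look worse. If the device truly reduces airway opening, mask handling can hide part of that benefit. Because type is not among the listed measurements, the components may not be separable afterwards. A reason such as desaturation does not reveal whether the response was a jaw thrust or a strap adjustment.

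**Working it through.** **No stated figure to reproduce.** The documents give no rate, effect size or power for airway maneuvers. Every rate below is an assumption; only the 62 per arm (Protocol 10.2, SAP 1.2) and the two-sided 0.05 level (Protocol 10.1, SAP 1.1) come from the plan.

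**Incidence model.** Let p be the proportion with at least one maneuver possible in both arms, taken as equal. Let q be the proportion of Group B with mask or strap handling, independent of other maneuvers. Then:

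- Group A incidence = p
- Group B incidence = 1 − (1 − p)(1 − q) = p + (1 − p)q
- Spurious excess in Group B = q(1 − p)

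For p = 0.2 to 0.6 and q = 0.1 to 0.3, the excess runs from 0.1 × 0.4 = 4 points to 0.3 × 0.8 = 24 points.

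**Chance of a significant result against the device**, p = 0.30 in both arms, by exact enumeration of two binomials with 62 per arm. Fisher's exact test is named in Protocol 5.2. The Pearson test is not named in the plan and is shown for comparison.

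| q | Group B incidence | Pearson | Fisher |
|---|---|---|---|
| 2% | 0.30 + 0.70 × 0.02 = 31.4% | 4% | 2% |
| 5% | 0.30 + 0.70 × 0.05 = 33.5% | 6% | 4% |
| 10% | 0.30 + 0.70 × 0.10 = 37% | 13% | 9% |
| 20% | 0.30 + 0.70 × 0.20 = 44% | 37% | 30% |
| 30% | 0.30 + 0.70 × 0.30 = 51% | 68% | 61% |

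With q = 0 the Pearson figure is 2.5%.

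**Masking of a true benefit.** Suppose shared maneuvers fall from 50% in Group A to 30% in Group B. With q = 0, 10% and 20%, Group B's all-maneuver incidence is 30%, 37% and 44%. Power to show the benefit is then 64%, 33% and 11% by Pearson, or 57%, 27% and 8% by Fisher.

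**Overlap.** Independence at p = 0.30 means that only 30% of patients with mask handling also have another maneuver. If 75% do, with q = 20%, the excess is 0.20 × 0.25 = 5 points. Group B incidence is 35%, and the Pearson chance against the device is about 8%, not 37%.

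**Crossover.** If a proportion x of Group A crosses to the mask and stays in Group A under intention-to-treat, the excess becomes q(1 − p)(1 − x). At p = 0.4 and q = 0.2 it is 12.0 points with no crossover, and 10.8, 9.6 and 7.2 points at 10%, 20% and 40%.

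**Number and duration.** Each adjustment adds to both, whether or not the patient had another maneuver. Overlap therefore gives no protection here. The documents offer no basis for a figure.

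**The case against.** A reader might infer that these items can occur only in the device arm and that the comparison is biased by definition. The documents do not support either statement. Section 5.4 allows Group A patients to cross over to the mask, and intention-to-treat keeps their later mask handling in Group A. Section 5.2 also mentions "oxygenation via a closed facemask" without tying it to an arm. A face mask used on a Group A patient can be pressed down too, although that patient already counts through mask ventilation. What the definition creates is unequal opportunity to score. A bias follows only if the adjustments occur, and for incidence only in patients with no other maneuver.

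The strongest counter-argument concerns purpose. If the endpoint is meant as total hands-on intervention, re-seating the mask is a real burden of the device, and leaving it out would favour the device. The protocol does not say which purpose it has. This stands, and it is why the all-maneuver comparison should be kept and why nothing here bars testing interface adjustments.

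A further inference would be that bag-mask ventilation, listed in Section 5.2 among the interventions ("supplement oxygen, bag-mask ventilation, and continuous nasal CPAP intra-operatively"), also loads the device arm. That sentence covers the whole study, and mask ventilation is possible in both arms, so it shows no device-only tilt. It does leave unclear when such ventilation is a study intervention and when it is an outcome event.

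It is also fair that the recorded reason might partly separate fit problems from obstruction, and that the open list might let an observer count cannula repositioning. The plan commits to neither.

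**Conclusion.** The point holds as an avoidable asymmetry in one secondary endpoint. Group B has extra opportunities to score, the tilt is against the device, and the listed measurements may not allow it to be undone later. Crossover weakens the tilt under intention-to-treat without removing it.

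The size cannot be determined from the documents. If mask handling is rare or mostly accompanies other maneuvers, the effect on incidence is small: with a 30% shared rate, about 4% to 8% by Pearson, against 2.5% with no tilt. If handling is independent and occurs in 20% to 30% of Group B, it is large, at 37% to 68%. These figures illustrate the range and do not predict what the trial will find.

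The primary desaturation comparison is not affected. This is a cheap improvement to a secondary endpoint.

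**What to change.** - Add a code to the case report form for the type of each maneuver, alongside number, duration and reason.
- In Protocol 5.3 and the SAP, prespecify a between-arm comparison of incidence, number and duration limited to maneuvers possible in both arms. Keep the all-maneuver comparison beside it, and say which question each answers.
- Report interface adjustments (mask, strap and cannula repositioning) separately by arm.
- Reconcile the listing of bag-mask ventilation as a study intervention in Section 5.2 with the counting of mask ventilation as an event in Section 5.3.

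The cost is protocol and SAP wording and one extra item to collect per maneuver. The restricted comparison will have fewer events.

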### An adverse event does not include:

- Medical or surgical procedures; the condition that leads to the procedure is not an adverse event
- Pre-existing disease, conditions, or laboratory abnormalities present at the start of the study that do not worsen in frequency or intensity
- Situations where an untoward medical occurrence has not occurred (e.g., hospitalizations for cosmetic or elective surgery or social/convenience admissions)
- Expected ICU course

Protocol #: IU IRB# 1810997768 Date: 31AUG21 Page 11 of 17

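### The airway-maneuver outcome counts a strap adjustment, a chin lift and an ETT as the same event and lists no maneuver type, so it can mask or reverse a difference in advanced airway support.

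*Protocol*

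**What the plan says.** Protocol section 5.3 opens the definition with the simple end of the range: "Airway maneuver: consists of either airway maneuvers such as chin lift, jaw thrust, submental pressure, mask ventilation". It continues with "pushing downward on the mask, tightening of the strap" and closes with "flexing the head forward or the insertion of a nasal or oral airway, supraglottic device, or ETT". There is no grade, tier or weight.

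Secondary outcome 5 (Summary Table, and Endpoints of Interest in section 1) reads: "Compare the incidence, duration, and reason for airway maneuvers". The measurement list in section 5.2 has "number of airway maneuvers performed, duration of airway maneuvers, reason for performing the airway maneuver". Which maneuver was used appears in neither place.

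Section 5.2 also fixes the comparator, "Group A: Standard care with a nasal cannula", and leaves the method open: "A statistician using student T-test, Fishers exact test, and other statistical methods they deem appropriate will analyze the collected data". Protocol section 10.3 and SAP section 1.3 do not mention airway maneuvers. The severity analysis there belongs to the desaturation outcome.

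**The concern.** Airway support is how the anesthesia team responds to the desaturation that the primary outcome measures. A reader of the results will want to know whether similar maneuver rates in the two arms hide more device insertions in one of them. As defined, the outcome cannot answer that.

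- **By incidence,** a patient with one brief chin lift and a patient who is intubated count the same.
- **By number,** a patient intubated at the first problem may count 1, while a patient with three short chin lifts counts 3.
- **By arm,** two of the listed items are adjustments to a mask and its strap. Group A wears a cannula, so these arise mainly in Group B, and routine fitting of the study device counts against it exactly as an ETT would.

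At stake is what secondary outcome 5 can conclude. A real benefit or harm in advanced airway support could be reported as no difference, or with the wrong sign.

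**Working it through.** The plan states no rate, power or sample size for airway maneuvers, so there is no figure of its own to reproduce. Two checks apply.

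**1. Can anything in the plan recover the level?**

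- Reason says why a maneuver was done, not which one it was.
- Duration does not rank intensity: a sustained jaw thrust can outlast a quick device insertion.
- The adverse-event log is not a reliable substitute, because its exclusions include "Medical or surgical procedures; the condition that leads to the procedure is not an adverse event".
- No analysis section reports by type or level.

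**2. What can pooling do?**

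From the documents: 62 patients per arm and two-sided alpha 0.05 (Protocol 10.1, SAP 1.1). Everything else is assumed: minor maneuvers in 40% of both arms; advanced support in 20% of Group A and 5% of Group B; a mask push or strap adjustment in a fraction s of Group B only; the three types independent.

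P(any maneuver) = 1 − product of (1 − p) over the types.

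- Group A: 1 − 0.60 × 0.80 = 0.520.
- Group B: 1 − 0.60 × 0.95 × (1 − s) = 1 − 0.57(1 − s).

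Power uses the normal approximation for two proportions: Φ[(|d|√n − 1.96√(2p̄q̄)) / √(pAqA + pBqB)].

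| s (Group B) | Any maneuver, A vs B | Power, pooled |
|---|---|---|
| 0% | 52.0% vs 43.0% | 17% |
| 10% | 52.0% vs 48.7% | 6% |
| 20% | 52.0% vs 54.4% | direction reversed |
| 40% | 52.0% vs 65.8% | direction reversed |

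Advanced support analysed separately, 20% versus 5%, has power of about 72% in every row. The direction turns where 0.57(1 − s) = 0.48, that is s = 1 − 0.48/0.57 ≈ 16%.

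Now let the device also cut minor maneuvers in Group B to 25%. Group B becomes 1 − 0.75 × 0.95 × (1 − s) = 1 − 0.7125(1 − s).

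- At s = 0: 52.0% versus 28.8%, pooled power about 76%. Pooling does little harm.
- At s = 40%: 52.0% versus 57.3%, reversed. The turning point is s = 1 − 0.48/0.7125 ≈ 33%.

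**3. Would an ordinal test of the highest level be a better main analysis?**

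Simulated power, 62 per arm, Fisher test on any maneuver against Wilcoxon test on highest level. The mixes are assumed percentages for none / manual / nasal or oral airway / mask ventilation / supraglottic device or ETT. Simulation error is a point or two.

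| Group A | Group B | Fisher | Wilcoxon |
|---|---|---|---|
| 20/40/20/15/5 | 30/50/12/6/2 | 20% | 66% |
| 20/40/20/15/5 | 20/60/12/6/2 | 2% | 40% |
| 40/42/10/6/2 | 65/25/6/3/1 | 77% | 77% |
| 30/55/8/5/2 | 55/30/8/5/2 | 78% | 60% |
| 40/54/3/2/1 | 40/56/2/1.5/0.5 | 3% | 5% |

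The ordinal test gains when advanced levels differ, ties in the third mix, and loses 18 points when only manual maneuvers differ. When advanced support is rare in both arms, neither test helps.

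**The case against.** The strongest reply is that section 5.2 is a prose list, not the CRF. The CRF is not in the documents, section 5.2 calls for an intraoperative record in every case, and section 12 has CRFs checked against source. Staff who note the reason and duration of a maneuver may well note which one it was. This stands. A reader might infer that the levels can never be separated afterwards, but the documents do not support that. They show only that type is not a listed measurement and that no use of it is prespecified. Even if type sits in the record, a grouping chosen after the data are seen is weaker than one fixed beforehand.

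A reader might also infer that simple maneuvers will occur in nearly every patient, so that the yes/no outcome sits at a ceiling. The documents give no maneuver rate. Their only related figure is 43% desaturation with a cannula, which is a different event.

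A third tempting reading is that an ordinal scale should replace the any-maneuver comparison. The simulations do not support that as a general rule. The ranking is also awkward: Group B's device is itself a mask on a hyperinflation bag, so where mask ventilation belongs is a judgement.

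Finally, the stakes are limited. This is one of 13 secondary outcomes, no power claim is attached to it, scope removal for a respiratory complication is captured separately in outcome 4, and the open wording on methods does not forbid a report by level. All true. But permission to report by level is not a plan to do so.

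**Conclusion.** The concern holds in a limited form. Followed as written, the incidence or number comparison in secondary outcome 5 can mask a real difference in advanced airway support and, in some mixes, reverse it. Mask adjustments counted in Group B are the clearest route to reversal.

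The size rests on assumed rates and on independence between maneuver types. In the main illustration, a fall in advanced support from 20% to 5% appears as 52% versus 43% (power about 17%, against about 72% analysed separately), and changes sign once about 16% of Group B needs a mask adjustment. If the device also reduces minor maneuvers and few mask adjustments occur, pooling costs little. So the distortion is possible, not inevitable. The primary desaturation result does not depend on it. This is a cheap improvement to a secondary outcome, not a flaw in the trial's main comparison.

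**What to change.** 1. Protocol 5.2: add the type of each airway maneuver to the recorded items. If the CRF already captures it, say so.
2. Protocol 5.3: put mask pushing and strap tightening in their own category, apart from airway-rescue maneuvers.
3. SAP 1.3, and the matching text in Protocol 10.3: keep the any-maneuver comparison. Before data review, prespecify a by-arm report of the proportion of patients with each category (mask adjustment; manual maneuver; nasal or oral airway; mask ventilation; supraglottic device or ETT) and of the highest level reached per patient.
4. Optionally, add an ordinal test of highest level (proportional-odds model or Wilcoxon) as a supportive analysis, not a replacement. State the assumed rank of mask ventilation and how mask adjustments are handled.

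The cost is one CRF field, a short addition to the SAP, and a grouping that involves some judgement and must be fixed in advance. Sample size, primary analysis and patient management do not change.
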